In patients receiving chronic therapy with dabigatran etexilate 110mg b.i.d., the median peak aPTT is approximately 57 sec [[U09-3249-02](#)]. Assuming the baseline range of normal is between 22 to 40 sec (aPTT assay as used in RE-LY) this peak aPTT prolongation corresponds to approximately 2 times control [[U11-1855-01](#)]. Twelve hours after the last dose, the median aPTT is approx. 1.7 times control [[U09-3249-02](#)], (median trough aPTT prolongation for patients receiving 110mg BID in RE-LY: 48 sec) given adequate renal function, with less than 10% of patients exceeding 2.4 times control [[U11-1855-01](#),[U09-3249-02](#)], (90th percentile trough aPTT prolongation for patients receiving 110mg b.i.d. in RE-LY: 69 sec). ECT shows a close linear correlation with the plasma concentrations of direct thrombin inhibitors, including dabigatran. Median ECT ratios over baseline of approx.1.8 at trough and 2.5 [[U11-1855-01](#)] at peak, have been observed after intake of dabigatran etexilate 110mg b.i.d. Coagulation times should be interpreted in relation to the timing of last drug intake of study medication (peak versus trough dabigatran levels). The

Proprietary confidential information.

© 2016 Boehringer Ingelheim International GmbH or one or more of its affiliated companies. All rights reserved.

This document may not - in full or in part - be passed on, reproduced, published or otherwise used without prior written permission.

current version of the IB should be referenced for further information about dabigatran etexilate.

Post Procedural Period:

With the exception of cardiac surgery, dabigatran etexilate will be initiated as soon as the patient is haemodynamically stable and haemostasis is achieved. If oral medication is not feasible, bridging therapy with i.v. or subcutaneous (s.c.) UFH or s.c. Low Molecular Weight Heparin (LMWH) should be considered at the discretion of the Investigator (see [Appendix 10.1](#)).

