4.2.1.5 Acute Coronary Syndrome

In patients with documented or suspected ACS, study drug should be temporarily discontinued if other anticoagulants (e.g. UFH) are deemed necessary. ASA, clopidogrel and glycoprotein IIb/IIIa inhibitors may be administered according to usual clinical practice.

Dabigatran Etxilate Treated Group:

In patients receiving dabigatran etexilate, unfractionated or low-molecular-weight heparin should be withheld until at least 12 hours have passed since the last dose of dabigatran etexilate or the aPTT is less than 1.5 x ULN.

- If the aPTT is between 1.2 and 1.5 x ULN, UFH may be commenced with or without a loading dose at the discretion of the physician and LMWH may be commenced at the usual therapeutic dose (without an i.v. loading dose)
- If the aPTT is above 1.5 times the ULN, it should be repeated every four hours until it falls below this level, after which heparin or other anticoagulation can be commenced.

Warfarin Treated Group:

Unfractionated or low-molecular-weight heparin (or other anticoagulants) may be administered in warfarin treated patients according to usual clinical practice.

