10.1.3 Bridging Therapy (e.g. for temporary interruptions of study drug due to interventions)

The use of bridging therapy depends on the thromboembolic risk status of the patient and the length of the planned interruption. It is at the discretion of the investigator whether to use a parenteral anticoagulant for bridging purposes or not.

Due to the short off- and onset of action, the majority of interventions in patients receiving dabigatran etexilate may not require the use of bridging therapy. If bridging therapy is deemed necessary for patients in the dabigatran etexilate arm, it is recommended to wait 12 hours after the last dose before switching from dabigatran etexilate to a parenteral anticoagulant.

Patients in the warfarin arm should be treated at the discretion of the investigator. In general, a parenteral anticoagulant may be considered when the INR is below the target INR. For recommendations how to switch back to study drug (dabigatran etexilate or warfarin) see Sections [10.1.1](#) and [10.1.2](#).

Proprietary confidential information.

© 2016 Boehringer Ingelheim International GmbH or one or more of its affiliated companies. All rights reserved.

This document may not - in full or in part - be passed on, reproduced, published or otherwise used without prior written permission.

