APPENDIX 10.2 SWITCHING FROM STUDY TREATMENT AT EOT

At the end of the study or if a patient discontinues early, continued anticoagulant therapy will usually be required because the patients has NVAf.

Investigators should plan for each subject's transition to standard of care taking into consideration the individual patient's risk profile and previous experience with non-study VKA.

As patients have different risk profiles, optimal approaches might differ between patients and not all possible approaches are described below.

OPTION 1: STARTING WARFARIN PRIOR TO DABIGATRAN ETEXILATE DISCONTINUATION

Start warfarin at the EOT visit and continue on dabigatran etexilate for 2-3 days after the EOT visit¹. In patients with CrCl >50mL/min who discontinue dabigatran but still require anticoagulation, dabigatran should be continued for three more days. For patients with moderate renal dysfunction (CrCl ≥30 to <50mL/min), as measured in the visit before EOT, dabigatran can be stopped after two days of concomitant VKA.

Many physicians will want to see warfarin naïve patients before starting warfarin. There is no special need to measure the CrCl before starting warfarin. If the INR is checked on the day of the EOT visit, Investigators should recognise that the presence of dabigatran could elevate the INR. Because dabigatran etexilate can increase the INR, the INR will better reflect warfarin's effect only after dabigatran etexilate has been stopped for at least 24 hours.

OPTION 2: BRIDGING WITH LMWH

Patient comes in on the day of the EOT visit, dabigatran etexilate is stopped and non-study VKA is started. LMWH can be used to bridge the patient until the INR becomes therapeutic. The LMWH can be started 12 hours after the last dose of dabigatran etexilate. This approach is an alternative to Option 1 described above.

The decision to use bridging therapy is at the discretion of the investigator (see [Appendix 10.1](#)).

Please consult local guidelines for the starting dose of the respective VKA.

Although there are large differences in the plasma half-lives of the various VKAs in clinical use, apart from the selection of the starting dose, the half-life of the VKA will have no impact on the transition from dabigatran etexilate.

¹ The date of final intake of dabigatran etexilate must be documented in the eCRF.

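### Section 4.2.1.5 gives opposite heparin instructions for a dabigatran patient with ACS who is past 12 hours from the last dose but still has aPTT above 1.5 x ULN

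*Protocol*

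**What the plan says.** Protocol Section 4.2.1.5 tells sites to stop study drug temporarily in documented or suspected ACS if another anticoagulant is needed. In the dabigatran group, UFH or LMWH is then withheld until "at least 12 hours have passed since the last dose of dabigatran etexilate or the aPTT is less than 1.5 x ULN".

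Two bullets follow. The first covers the intermediate range: "If the aPTT is between 1.2 and 1.5 x ULN, UFH may be commenced with or without a loading dose", with LMWH also allowed. The second covers the upper range: "If the aPTT is above 1.5 times the ULN, it should be repeated every four hours until it falls below this level". Neither bullet mentions time since the last dose. Warfarin patients are managed by usual practice, with no time or aPTT condition.

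Appendix 10.1.3, on bridging during temporary interruptions, gives a time condition with no aPTT condition: "it is recommended to wait 12 hours after the last dose before switching from dabigatran etexilate to a parenteral anticoagulant". Appendix 10.2 uses the same interval for LMWH at the end of treatment: "The LMWH can be started 12 hours after the last dose of dabigatran etexilate".

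Section 4.2.1.3 (elective surgery) supplies the aPTT values used below.

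**The concern.** The lead sentence joins time and aPTT with *or*, so passing 12 hours is enough to end the hold whatever the aPTT. The second bullet makes aPTT decisive and attaches no time limit. For a patient past 12 hours with a high aPTT, a site reading the sentence may start heparin, and a site reading the bullet must keep testing and wait.

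The stake is mainly patient safety. Section 4.2.2.1 says that UFH or LMWH together with dabigatran has not been studied and may raise bleeding risk. All patients have recently been stented, and the rule concerns the dabigatran arms only. A resulting bleed would count in the primary analysis, which follows all randomised patients (Protocol 7.3.1). It would usually count in the on-treatment analysis too, because that analysis ignores temporary interruptions (SAP 7.4).

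**Working it through.** **1. The instructions by time and aPTT**

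| Time since last dose | aPTT | Lead sentence, 4.2.1.5 | Bullets, 4.2.1.5 | Appendix 10.1.3 |
|---|---|---|---|---|
| under 12 h | below 1.5 x ULN | release | first bullet permits heparin at 1.2 to 1.5 x ULN | recommends waiting |
| under 12 h | above 1.5 x ULN | hold | hold | recommends waiting |
| 12 h or more | below 1.5 x ULN | release | first bullet permits heparin at 1.2 to 1.5 x ULN | waiting time met |
| 12 h or more | above 1.5 x ULN | **release** | **hold** | waiting time met |

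Only the last row contains opposite instructions within one section. The first row shows a difference between the section and the appendix.

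**2. Inputs, all from Section 4.2.1.3, 110mg b.i.d.**
- Normal range: "Assuming the baseline range of normal is between 22 to 40 sec" (the RE-LY assay), so ULN = 40 s.
- Median 12-hour trough: 48 s, stated as about 1.7 times control.
- 90th-percentile trough: 69 s, stated as 2.4 times control.
- Median peak: about 57 s, stated as about 2 times control.

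**3. Reproducing the protocol's multiples**

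Implied control values are 57/2 = 28.5 s, 48/1.7 = 28.2 s and 69/2.4 = 28.75 s. These agree with one another and lie inside 22 to 40 s, so the figures are coherent. They are multiples of control, whereas Section 4.2.1.5 uses multiples of ULN, so they must be converted.

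**4. Conversion to the ULN scale**
- Cut-off: 1.5 x 40 = 60 s.
- Median trough: 48/40 = 1.20 x ULN.
- 90th-percentile trough: 69/40 = 1.725 x ULN.

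**5. Share in conflict at 12 hours**

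Bounds without any distributional assumption: 10% of patients lie at or above 69 s, which exceeds 60 s, so at least 10% are above the cut-off. The median of 48 s is below 60 s, so no more than 50% are.

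Illustrative log-normal fit to the median and 90th percentile:
- sigma = ln(69/48)/1.2816 = 0.283
- P(aPTT > 60) = 1 − Φ(ln(60/48)/0.283) = 0.215, about 22%

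A normal fit gives SD = (69 − 48)/1.2816 = 16.4 s and 1 − Φ(12/16.4) = 0.232, about 23%.

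**6. Dependence on the assumed ULN**

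Holding the aPTT values in seconds fixed, the 10% lower bound stands for any ULN below 69/1.5 = 46 s.

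**The case against.** The best defence is that the bullets only explain how to use the aPTT condition when heparin is wanted before 12 hours. On that reading the second bullet lapses at 12 hours and nothing conflicts. It is a natural reading, but the text does not state it and a site could as reasonably read the bullet as a standing limit. The discretion in the section does not settle the matter either: it covers the use of a UFH loading dose, not which condition governs. It is also fair to say that divergent site behaviour is a risk and has not been shown.

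Three stronger inferences are tempting, and the documents do not support them.

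- *That the rule contradicts the protocol by releasing heparin at peak effect in more than half of 110mg patients.* Section 4.2.1.3 says "the median peak aPTT is approximately 57 sec", and 57 s is below 60 s (57/40 = 1.43 x ULN). But early release on the aPTT limb is what an *or* rule permits, and the first bullet agrees with it. Whether the cut-off is suitable is a clinical judgement. The gap is 3 s, it rests on an approximate median and an assumed assay range, and it reverses if ULN is below 57/1.5 = 38 s. No peak spread is given. Section 4.2.1.3 also tells readers to interpret coagulation times in light of when the last dose was taken.
- *That Appendix 10.1.3 flatly contradicts Section 4.2.1.5.* The appendix gives a recommendation on bridging, which it leaves to investigator discretion, and Section 4.2.1.5 does not cite it. The two differ before 12 hours and should be aligned, since Section 4.2 sends temporary interruptions to Appendix 10.1. That is looser than a conflict of requirements.
- *That the primary comparison is biased.* The documents do not say how many patients will have ACS on dabigatran, need heparin and fall in the conflicting window, so no effect on the hazard ratio can be derived.

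**Conclusion.** The contradiction within Section 4.2.1.5 is real and can be read directly from the text. It arises past 12 hours with aPTT above 1.5 x ULN. On the protocol's own 110mg values, at least 10% and at most 50% of patients have such an aPTT at 12 hours; about 22% is an illustration that depends on the log-normal shape.

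These shares describe 110mg patients at 12-hour trough, not the fraction of trial patients who will meet the problem; that fraction is unknown. They assume the RE-LY assay range. The protocol states its 12-hour values for adequate renal function, and the trial enrols down to a CrCl of 30 mL/min. No aPTT values are given for 150mg.

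The approximate peak median of 57 s is a secondary observation for the sponsor's clinicians to have in view, not a contradiction. Nothing here changes the estimand, the analysis or the power. The point should be fixed because opposite instructions on combining two anticoagulants can be removed by wording alone. It does not threaten the trial's conclusions.

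**What to change.** Reconcile the lead sentence and the second bullet of Section 4.2.1.5 so that the text:

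1. states whether the time and aPTT conditions are alternatives or must both hold;
2. gives one instruction for a patient past 12 hours with aPTT above 1.5 x ULN;
3. cross-refers to Appendix 10.1.3 and says how its 12-hour recommendation applies in ACS.

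The clinical experts doing this should have the peak and trough aPTT values of Section 4.2.1.3 before them. Which rule applies is theirs to decide. The cost is wording in a protocol amendment or a letter to sites, with no added visits, tests or patients.

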Dabigatran etexilate can be re-commenced at the cessation of parenteral anticoagulant treatment according to the same regimen as at randomisation, provided clinically indicated and in accordance with the recommendations in [Appendix 10.1](#).

For patients randomised to Warfarin, refer to [Section 4.2.1.3](#).

4.2.1.7 Overdose

Overdose following administration of dabigatran etexilate may lead to haemorrhagic complications due to its pharmacodynamic properties. In cases of suspected overdose it may be advisable to assess the anticoagulation status of a patient. A TT measure with the calibrated Hemoclot[®] thrombin inhibitor assay indicating a dabigatran plasma concentration of >200ng/mL (approximately >65 seconds) prior to the next drug intake after 150mg twice-daily dosing (trough measure, i.e. 10-16 hours after the last drug intake) may be associated with an increased risk of bleeding. An aPTT test may be useful to assist in determining an excess of anticoagulant activity, despite its limited sensitivity. An aPTT > 2-fold ULN at trough, i.e. when the next dose is due, may be associated with a higher risk of bleeding.

For a summary how to manage bleeding events on dabigatran etexilate see also [Section 4.2.1.1](#) and corresponding [Figure 4.2.1.1: 1](#).

Specific reversal agent to dabigatran

A specific reversal agent (idarucizumab) has been developed and is currently available in many countries and being reviewed for registration in various other countries. When clinically indicated and available, it can be given to a patient in the context of a clinical trial (e.g. BI trial 1321.3) or from commercial supply when it becomes approved. If the specific reversal agent for dabigatran is given, information surrounding the clinical circumstances, treatment and clinical outcome will be collected on the eCRF of the appropriate trials.

Proprietary confidential information.

© 2016 Boehringer Ingelheim International GmbH or one or more of its affiliated companies. All rights reserved.

This document may not - in full or in part - be passed on, reproduced, published or otherwise used without prior written permission.

4.2.2 Restrictions

4.2.2.1 Restrictions regarding concomitant treatment

Corticosteroids or NSAIDs may be used if clinically indicated according to current treatment guidelines but it is strongly recommended to avoid these if possible. It should be noted that the use of any of these agents with warfarin or dabigatran etexilate is likely to increase the risk of bleeding.

The following treatments should not be taken during the active treatment phase of the trial:

1. Treatment with ticlopidine or prasugrel
2. Fibrinolytic agents (see [Section 4.2.1.4](#) for exception)
3. GPIIb/IIIa antagonists (e.g. abciximab, tirofiban)
4. Treatment with systemic ketoconazole, itraconazole, posaconazole, cyclosporine, tacrolimus, dronedarone and rifampicin, phenytoin, carbamazepine or St. John's Wort
5. Dipyridamole, rivaroxaban, apixaban and edoxaban, or other oral anticoagulants (e.g. VKAs)
6. ASA - except where specified in the protocol for patients randomised to the warfarin arm or in both treatment arms after 12 months of treatment if clopidogrel or ticagrelor is switched to ASA ($\leq 100\text{mg q.d.}$) at Investigator discretion. The patients should be advised to not use additional ASA-containing over-the-counter medications.

The Investigator is alerted to the use of concomitant administration of moderate to strong P-gp inhibitors (e.g. such as amiodarone, verapamil, quinidine, nelfinavir, posaconazole, ritonavir, saquinavir and tipranavir+ritonavir or lopinavir+ritonavir) or P-gp inducers in this study due to a potential risk of higher or lower plasma levels of dabigatran and consequent exaggerated or reduced pharmacodynamic effect of dabigatran etexilate (notably bleeding risk). Concomitant use of such drugs is not prohibited in this study *per se* (except for treatment with ketoconazole, itraconazole, posaconazole, cyclosporine, tacrolimus, dronedarone, rifampicin, phenytoin, carbamazepine or St. John's Wort), but should be used with caution or, at Investigator discretion, switched to a suitable alternative.

In the RE-LY study, patients treated concomitantly with verapamil had on average at trough and two hours post-dose dabigatran plasma concentrations increased by only 16% and 20%, respectively. Accordingly, the annualised bleeding rates in patients who had used verapamil at least once together with warfarin, dabigatran etexilate 110mg b.i.d. or 150mg b.i.d. were 3.33%, 3.09% and 3.92%, respectively. If verapamil is initiated during the course of this trial in a patient randomised to receive dabigatran etexilate 150mg b.i.d., consideration to separate the timing of administration of dabigatran etexilate and verapamil should be given.

Proprietary confidential information.

© 2016 Boehringer Ingelheim International GmbH or one or more of its affiliated companies. All rights reserved.

This document may not - in full or in part - be passed on, reproduced, published or otherwise used without prior written permission.

If dabigatran etexilate is given at least two hours before verapamil for the first three days, the increase of dabigatran exposure will be reduced compared to taking verapamil and dabigatran etexilate at the same time-point.

In the RE-LY study, concomitant administration of amiodarone or quinidine and dabigatran etexilate did not increase the relative risk of bleeding compared to patients on warfarin and amiodarone or quinidine. Therefore, no dose adjustment of dabigatran etexilate is considered necessary in this study for patients receiving amiodarone or quinidine as co-medications.

The strong P-gp inducer rifampicin (and potentially also carbamazepine, phenytoin or St. John's Wort) is associated with a potential risk of lower plasma levels of dabigatran (in a Phase I trial rifampicin decreased total dabigatran peak plasma concentration and total exposure (AUC) by 65.5% and 67%, respectively) and consequent reduced pharmacodynamic effect of dabigatran etexilate (notably increased thromboembolic risk) and should therefore not be taken during the course of this trial.

A list of common P-gp inhibitors will be provided in the ISF.

The concomitant use of dabigatran etexilate with the following treatments has not been studied and may increase the risk of bleeding: UFHs (except at doses necessary to maintain patency of central venous or arterial catheter) and heparin derivatives, low molecular weight heparins (LMWH), fondaparinux, desirudin, thrombolytic agents, GPIIb/IIIa receptor antagonists, ticlopidine, dextran, sulfapyrazone, rivaroxaban, apixaban, edoxaban, prasugrel, direct thrombin inhibitors, VKAs and the P-gp inhibitors itraconazole, tacrolimus, cyclosporine, ritonavir, tipranavir, nelfinavir and saquinavir.

Bleeding risk may be increased in patients concomitantly treated with selective serotonin re-uptake inhibitors ([U11-1642-01](#)) or selective serotonin norepinephrine re-uptake inhibitors ([U12-1072-01](#)).

Co-administration of oral anti-platelet (including ASA) and NSAID therapies increase the risk of bleeding ([U09-3249-02](#)). Specifically, with concomitant intake of antiplatelets or strong P-gp inhibitors in patients aged ≥ 75 years, the risk of major bleeding, including GI bleeding, increases.

If bleeding is clinically suspected, appropriate measures such as testing for occult blood in stool, or testing for a drop in haemoglobin is suggested ([U12-1072-01](#)). Investigators should assess the benefit-risk of the concomitant use of drugs that can promote bleeding, e.g., NSAIDs, corticosteroids and ASA, other anticoagulants and use them only when the benefits are thought to outweigh the risks.

4.2.2.2 Restrictions on diet and life style

Dabigatran etexilate can be taken with or without food. There are no specific dietary restrictions with dabigatran etexilate, whereas patients randomised to VKA need to follow dietary instructions regarding their vitamin K intake. They must also be aware of the potential risk of over- or under dosing with changes of co-medications (e.g. use of antibiotics) or concomitant diseases (e.g. diarrhoea).

Proprietary confidential information.

© 2016 Boehringer Ingelheim International GmbH or one or more of its affiliated companies. All rights reserved.

This document may not - in full or in part - be passed on, reproduced, published or otherwise used without prior written permission.

4.3 TREATMENT COMPLIANCE

Patients are requested to bring all remaining trial medication including empty package material with them when attending visits.

Dabigatran Etexilate:

Based on capsule counts, treatment compliance will be calculated as the number of capsules taken, divided by the number of capsules which should have been taken according to the scheduled period, multiplied by 100.

Doses taken on the current visit day will be excluded from the count and doses taken on the previous visit day will be included in the count.

$$\text{Treatment compliance (\%)} = \frac{\text{Number of tablets actually taken} \times 100}{\text{Number of tablets which should have been taken}}^1$$

A patient will be considered as non-compliant if the number of doses taken is not between 80-120% of the expected number of doses. If compliance does not meet this range the patient should be asked to provide an explanation and re-informed about the purpose and conduct of the trial. Non-compliance should be discussed with BI.

General principles regarding the evaluability of non-compliant patients are outlined in [Section 7.3](#). Decisions about evaluability of patients will be made at the Blinded² Report Planning Meeting (BRPM) and at the latest prior to database lock.

Warfarin:

Warfarin compliance will be monitored by means of the INR rather than by pill counts as it is a more accurate and biologic measure of pharmacodynamic effect than pill counts. Investigators will be able to assign INR monitoring to a clinic outside the investigational site and dose adjustments will be made according to usual clinical practice. However, the Investigator will be responsible for reporting INR results, dose management of the patient and drug accountability of the warfarin prescribed. Patients must have the INR measured at least every two weeks for first three months, when commencing warfarin for the first time, otherwise at least monthly measurement are required. More frequent INR measurements may be done as necessary at the discretion of each Investigator or anticoagulation clinic. To aid Investigators, a validated nomogram, will be provided in the ISF, which will indicate recommended dose changes and INR re-testing times for different INR values. This nomogram requires more frequent INR monitoring after out-of-range INR values have occurred.

The quality of warfarin therapy for each patient will be assessed by reporting the number of INR values within the indicated therapeutic target range (2.0 – 3.0 and 2.0 – 2.5) as well as those above and below this range. The Rosendaal method [[R08-1695](#)] will be used to evaluate the percentage of time that a patient's INR is in range (i.e. time in therapeutic range

¹ The number of tablets which should have been taken should take into account any temporary interruptions in study drug

² Despite the trial being open label, the trial team will be blinded during medical quality review.

(TTR)). For each calendar month, the mean of all INR values will be reported. This will be calculated for each patient, for each centre, for each country and for the whole study. The mean percentage of time of INR in range will be calculated for each centre and each country during the trial conduct to monitor the INR control. The percentage of time of INR in range for each country and for the trial will be reported at study end.

Analyses from clinical trial data for SPAF have identified a minimum threshold of TTR of at least 60%, below which warfarin may be considered as no more effective than DAPT [[P07-02268](#)]. The goal for the study is that the INR control should be at least as good as that achieved for anticoagulation in the historical control studies. The mean TTR [INR 2.0-3.0] for warfarin in RE-LY was 64% (median 67%) [[U09-3249-02](#)].

Proprietary confidential information.

© 2016 Boehringer Ingelheim International GmbH or one or more of its affiliated companies. All rights reserved.

This document may not - in full or in part - be passed on, reproduced, published or otherwise used without prior written permission.

